#### 4.11.2.3 Evaluation of IM Impact on Selected PK, PD, Efficacy, and Safety Measures

- The impact of IM on selected PK, PD, efficacy, and safety measures will be evaluated by stratifying plasma PK exposure measures (such as plasma trough and post-treatment olezarsen concentrations, etc.), selected PD, clinical efficacy endpoints and safety measures by patient level ADA data, summarized using typical descriptive statistics, and presented graphically and/or in tables. Efficacy measures to be stratified by patient level ADA data will include but may not be limited to apoC-III and TG levels. Safety measures to be stratified by patient level ADA data will include but may not be limited to AEs, and lab tests for hematology, liver and kidney functions, as appropriate.

Lastly, other stratifications (e.g., based on antibody titer, onset of ADA, patient ADA status at baseline, etc.) of selected PK, efficacy and safety assessments may also be performed if deemed warranted at the discretion of the pharmacokineticist, medical monitor, and/or biostatistician.

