### Plasma Trough and Post-Treatment Sampling Schedule for all Patients

	Treatment Period						Follow-up Period		
Study Week	1	5	13	25/ET-L1**	37	53/ET-L4** or Tx ET	4*	8*	13/ Post-Tx ET*
Study Day	1	29	85	169	253	365	28*	56*	91*
	Pre-dose	Pre-dose	Pre-dose	Pre-dose	Pre-dose	Any time	PK only Any time	PK only Any time	Any time

\*Weeks/days from end of treatment. End of treatment is defined as 1 dosing interval (4 weeks) post-last dose

\*\*Landmark visit. For early termination (ET-L) visits: Week 25 is ET-L1 and Week 53 is ET-L4

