#### 4.11.2 Immunogenicity (IM) Analysis

##### 4.11.2.1 Sample Level ADA Data

Samples collected for IM assessment at baseline (Day 1 pre-dose), during treatment and post-treatment follow-up period including early termination samples will be analyzed for anti-olezarsen antibodies (ADA).

An evaluable sample will be designated 'Positive' based on both positive screening and confirmation assay results (i.e., confirmed positive result), and otherwise will be deemed 'Negative'. An unevaluable sample, for example, a sample not being stored properly, or insufficient volume for analysis, will be reported as "unknown". Sample ADA results (screen positive/negative, confirmed positive/negative or unknown, and when applicable, titer of anti-olezarsen antibodies) before, during, and after treatment with study drug (olezarsen or placebo) (sample ADA status) will be listed by treatment, dose, and day of collection.

The sample ADA incidence (number) and incidence rate (percent) at each evaluated study time point will be determined and appropriately summarized as the total number of and percentage of evaluated subjects with sample ADA negative, positive, and unknown status. Furthermore, titer over time will be also appropriately summarized (using descriptive statistics) as median, quartiles (25% and 75%), and range by treatment and dose.

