##### 4.11.2.2 Patient Level ADA Data

Patient overall ADA status (ADASTAT) will be defined as 'Positive' status if they have at least one confirmed positive sample result at any time during the treatment or post-treatment evaluation periods; 'Negative' status if all evaluated ADA sample results during the treatment and post-treatment evaluation periods are ADA negative and they have at least one evaluable ADA result collected post study drug treatment. Otherwise, patient overall ADA status will be assigned 'Unknown'.

Furthermore, patients with positive overall ADA status may be further classified into different ADA types (ADATYPE) based on their baseline ADA status and change in ADA titer post-treatment as described below ([Shankar et al., 2014](#)):

- Treatment-Emergent ADA: subjects with either treatment-induced ADA or treatment-boosted ADA as described below:
  - Treatment-Induced ADA: ADA developed de novo (seroconversion) following study drug administration (i.e., formation of ADA any time after the initial drug administration in a subject without pre-existing ADA, i.e., baseline negative ADA)
  - Treatment-Boosted ADA: pre-existing ADA that were boosted to a higher level following study drug administration (i.e., any time after the initial drug administration the ADA titer is greater than the baseline titer by a factor of 8-fold or more)
- Treatment-Unaffected ADA: pre-existing ADA that were not affected (boosted) following biologic drug administration (i.e., any time after the initial drug administration the ADA titer is 4-fold or less)
- For patients with negative overall ADA status, ADATYPE would be classified as baseline negative or baseline positive, based on their baseline ADA status.

Other patient level IM parameters to be calculated/defined may include but not limited to:

- ADA category (ADACAT) will include subjects with Negative, Treatment-Unaffected, and Treatment-Emergent ADA status as described above.
- Patient ADA Status at Baseline (ADASTATB): "Positive" if the subject has Week 1 Day 1 pre-dose sample (baseline) tested as confirmed positive; "Negative" if the patient has Week 1 Day 1 pre-dose sample (baseline) tested as confirmed negative; "Unknown" if the patient has Week 1 Day 1 pre-dose sample (baseline) unevaluable.
- First day of ADA detected (TFSTADA): i.e., the first day positive ADA sample was observed, will be calculated by: the date of first sample has "positive" sample IM status - first dose date +1.

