- Onset of treatment-emergent ADA (ONSETTE): i.e., the first day treatment-emergent ADA (treatment-induced or treatment-boosted ADA) was observed, will be calculated by:
  - For treatment-induced ADA: the date of first sample has "positive" sample IM status - first dose date +1
  - For treatment-boosted ADA: the date of the first sample has ADA titer greater than the baseline titer by a factor of 8-fold or more – first dose date +1
- Last Positive ADA Study Day (TLSTADA): defined as the last positive ADA sample observed from the start of study drug treatment and will be calculated by: the date of last sample has "positive" sample IM status - first dose date +1
- Last IM Sampling Study Day (TLSTSAMP): defined as the last ADA sample collected from the start of study drug treatment and will be calculated by: the date of last sample collected - first dose date +1
- Duration of treatment-emergent ADA (DURTE): i.e., the total duration of treatment emergent ADA during the study, and will be calculated using the last sample result carried forward. This parameter will be calculated for patients with treatment-induced ADA and treatment boosted ADA.
- Peak titer (PEAKTIT): the highest titer observed for the patient

- Time to peak titer (TPEAKTIT): the time to reach peak titer will be calculated by: the date of first peak titer observed- first dose date +1
- Total number of ADA Positive Samples (NOPOSAMP): the total number of ADA samples being confirmed positive for the patient
- Total number of ADA Samples evaluated (NOADASAMT): the total number of ADA samples being collected and analyzed successfully with reportable results for the patient

Lastly, patients with positive ADA status may further be classified as being transient or persistent ADA response, if there are sufficient number of patients with transient ADA status. Transient and persistent ADA definitions are defined below and based on [Shankar et al., 2014](#):

- Transient ADA response:
  - Treatment-induced ADA detected only at one sampling time point during the treatment or follow-up observation period (excluding the last sampling time point, which will be considered persistent unless shown to be undetectable at a later time) or

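### The antibody-by-efficacy summaries default to whole-study ADA status, so patients first found positive after Week 25 can be counted as ADA-positive at Month 6

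*Combined protocol and SAP*

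**What the plan says.** SAP 4.11.2.2 classes a patient's overall ADA status as positive "if they have at least one confirmed positive sample result at any time during the treatment or post-treatment evaluation periods". No cut-off is tied to an efficacy visit. The other main groupings in that section, ADA type and ADA category, also run over the whole study, because treatment-emergent ADA may arise at any point after the first dose.

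SAP 4.11.2.3 then splits PK exposure, PD, efficacy and safety results by patient-level ADA data: "Efficacy measures to be stratified by patient level ADA data will include but may not be limited to apoC-III and TG levels". The results are to be "summarized using typical descriptive statistics, and presented graphically and/or in tables". SAP 4.11.1 likewise summarizes plasma concentrations by study day, with and without stratification by subject-level ADA data.

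Two time-aware elements exist. SAP 4.11.2.2 lists an onset variable, ONSETTE, defined as "the first day treatment-emergent ADA (treatment-induced or treatment-boosted ADA) was observed". SAP 4.11.2.3 allows "other stratifications (e.g., based on antibody titer, onset of ADA, patient ADA status at baseline, etc".), but only at the discretion of the pharmacokineticist, medical monitor or biostatistician. SAP 4.11.2.1 adds a by-visit count, "The sample ADA incidence (number) and incidence rate (percent) at each evaluated study time point will be determined", which is not crossed with efficacy.

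The protocol's Appendix C table, "Plasma Trough and Post-Treatment Sampling Schedule for all Patients", places ADA samples at Day 1 pre-dose, Weeks 5, 13, 25, 37 and 53, and follow-up Week 13. Follow-up Weeks 4 and 8 are for PK only. Month 6 lipids are the average of Weeks 25 and 27 (SAP 4.2.2).

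**The concern.** The default grouping uses later information to label earlier outcomes. A patient negative at Weeks 5, 13 and 25 and first positive at Week 37 or later would be shown as ADA-positive in a Month 6 TG or apoC-III summary. The same applies to a plasma trough taken before the antibody was found. If antibodies blunt TG lowering, mixing such patients into the positive group makes the blunting look smaller than it is.

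Safety has a related time-order problem. Adverse events and laboratory abnormalities that precede the first positive sample are still shown under ADA-positive.

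At stake is the SAP's own assessment of whether antibodies matter for efficacy, exposure and safety. Protocol 10.6.4 lists that assessment as part of the immunogenicity analysis.

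**Working it through.** The documents give no ADA incidence, onset distribution or dilution figure, so there is no stated figure to reproduce. The schedule is taken from the documents; the onset patterns are assumptions.

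**Inputs.** Scheduled post-baseline ADA days (protocol Appendix C): 29, 85, 169, 253, 365, and 365 + 91 = 456. Samples at or before Week 25: 3 of 6. Samples at or before Week 53: 5 of 6.

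**Formula.** Let f be the share of ever-positive patients already found positive by Week 25. Let μ₊ and μ₋ be the Month 6 means with and without antibodies. Assume that antibodies found later have no effect at Month 6 and that late converters otherwise resemble never-positive patients. Then:

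- ever-positive mean = f·μ₊ + (1 − f)·μ₋
- never-positive mean = μ₋
- observed contrast = f·(μ₊ − μ₋), so the share lost is 1 − f

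**Onset patterns.** C is the assumed proportion ever positive.

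- Equal conditional chance at each sample: f = [1 − (1 − C)^(3/6)] / C
- Constant hazard to Day 456: f = [1 − (1 − C)^(169/456)] / C
- Exponential onset truncated at Day 456, with λ = ln 2 / median (median before truncation): f = (1 − e^(−169λ)) / (1 − e^(−456λ))

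| Assumed pattern | f | Contrast lost |
|---|---|---|
| First positivity equally likely at each of 6 samples | 3/6 = 0.50 | 50% |
| Equal conditional chance per sample, C = 5% to 60% | 0.51 to 0.61 | 49% to 39% |
| Constant hazard, C = 5% to 60% | 0.38 to 0.48 | 62% to 52% |
| Exponential, median 57 days | 0.875 | 12.5% |
| Exponential, median 85 days | 0.77 | 23% |
| Exponential, median 113 days | 0.69 | 31% |
| Exponential, median 169 days | 0.59 | 41% |
| Exponential, median 253 days | 0.52 | 48% |

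The two ends, with numbers put in:

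- Constant hazard, C = 0.05: (1 − 0.95^0.371) / 0.05 = 0.377, so 62% is lost.
- Exponential, median 57 days: λ = 0.01216, and (1 − e^(−2.055)) / (1 − e^(−5.545)) = 0.872 / 0.996 = 0.875, so about 12% is lost.

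On this range, a hypothetical true 10-point loss of TG effect in antibody-positive patients would appear as about 4 to 9 points at Month 6 (10 × 0.38 to 10 × 0.875).

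**Month 12.** If first positivity is equally likely at each sample, f = 5/6 = 0.83 and about 17% is lost.

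**With status cut at Week 25.** f = 1 for Month 6, and this source of dilution disappears.

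**Precision of onset.** From Day 1 the gaps between scheduled samples are 4, 8, 12, 12, 16 and 13 weeks, so onset is known only to within 4 to 16 weeks.

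**The case against.** The strongest reply is that SAP 4.11.2.3 names neither Month 6 nor overall ADA status as the stratifier. Section 4.11.2.2 lists many patient-level variables, including the onset date. This is correct: the link to Month 6 is an inference from the primary endpoint and the by-visit lipid summaries. It does not remove the problem. The main alternative groupings, ADA type and ADA category, are also whole-study, and onset appears only among the optional extra stratifications.

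A reader might infer that the Month 6 contrast is cut by about half. The documents do not support that figure. It matches the count of three late samples in six, but it needs roughly flat onset; early onset gives far less dilution. The constant-hazard case also keeps the on-treatment rate running through follow-up, although dosing ends at Week 49 (protocol 8.1). In addition, antibody first detected at Week 37 could have arisen before the Week 27 lipid draw, in which case the late converter is not wholly misclassified.

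A reader might also infer that early stoppers are more often called negative because they have fewer samples. Protocol 8.7.1 and Appendix C give them ADA sampling at treatment early termination, at the Week 25 and Week 53 landmark visits, and at the end of follow-up. Any shortfall depends on attendance and cannot be sized from the documents.

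On safety, protocol 8.5.5 and 8.5.6 call for ADA testing of patients with persistent or increasing constitutional symptoms or possible hypersensitivity, and SAP 4.11.2.2 does not set such samples apart. Having an event can therefore raise the chance of being classed positive. Splitting time at onset does not fully cure this.

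**Conclusion.** The point holds as a misalignment in a descriptive analysis. Following the default groupings, patients not yet found positive by Week 25 can be counted as ADA-positive at Month 6, which moves the contrast toward no difference. The loss is roughly 12% to 62% at Month 6 across the assumed onset patterns. At Month 12 it is about 17% if first positivity is equally likely at each sample. Both figures assume that later-detected antibodies had no effect at the earlier visit. The loss is zero if nobody first turns positive after the visit concerned.

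It would go too far to say that the plan will report no antibody effect, or that the efficacy conclusions are at risk. The summaries involve no test or model and lie outside the hierarchy in SAP 4.9.1.5, so alpha, power and every primary and secondary comparison are untouched. The change is still worth making, because the mandatory summary is the misaligned one and the time-aware option has no stated trigger.

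**What to change.** In SAP 4.11.2.3:

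- **Month 6 efficacy, and PK up to that visit:** require an ADA status based on confirmed samples through Week 25.
- **Month 12 efficacy:** require a status based on confirmed samples through Week 53.
- **Incidence table:** keep ever/never status there.
- **Adverse events and laboratory abnormalities:** add event rates before and after treatment-emergent onset (ONSETTE). State that onset is known only to within the sampling interval and that event-triggered ADA samples may affect classification.

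A Week 25 cut still looks ahead for the Week 5 and Week 13 troughs; the table footnote should say so.

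No new samples are needed. The visit-aligned status is a new derivation from results already scheduled. SAP 4.11.2.2 lists ONSETTE among parameters that may be calculated, so its derivation should be made definite. The cost is SAP wording, modest programming and a smaller, less precise ADA-positive group at Month 6.

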#### *4.11.3 Additional/Exploratory Analyses*

##### *4.11.3.1 The Adjudicated MACE Incidence Rates*

The adjudicated MACE incidence rates (number and percent of subjects), exposure adjusted incidence (EAIR) and event rates (EAER) will be summarized by treatment group and total olezarsen treated. Additional analyses of MACE composite of CV death, non-fatal MI, non-fatal ischemic stroke, or arterial revascularization (coronary or non-coronary), and the triple composite of CV death, non-fatal MI, or non-fatal ischemic stroke may be performed depending on rates of MACE. The event rate will be calculated as number of adjudicated treatment emergent MACEs divided by the total duration of follow-up time.

##### *4.11.3.2 Summary of Lipid Parameters*

All lipid data including results, absolute changes and percent changes from Baseline will be summarized using descriptive statistics by treatment group, total olezarsen treated and study visit. The means plus/minus SEMs for results, absolute changes and percent changes will be plotted over time by treatment group.

##### *4.11.3.3 Response Rates*

The response rates based on various TG threshold (fasting TG < 135 mg/dL; < 150 mg/dL; > 2000 mg/dL in subgroup of patients with baseline fasting TG ≤ 2000 mg/dL) and TG percent reductions (≥ 40%, ≥ 50%, ≥ 60%, ≥ 70% reduction) at Month 6 and Month 12 will be compared between each olezarsen treatment group and pooled placebo group using a logistic regression model with the treatment group and natural log transformed baseline fasting TG as a covariate. Missing TG values will be imputed using the same multiple imputation method as the primary analysis of the primary endpoint.

## **4.12 Determination of Sample Size**

With 33 patients in each olezarsen treatment group and 22 in the placebo group, there would be an approximately 80% power to detect a 60% difference between each olezarsen treatment group and placebo group at an alpha level of 0.05 (two-sided), assuming 60% reduction in the olezarsen treatment patients, no change in the placebo patients, and a common SD of approximately 73%.

Approximately 152 patients will be enrolled in this trial to account for potential early dropouts.

## **4.13 Changes to Protocol-planned Analyses**

In protocol, it states: 'All primary and secondary endpoints will be assessed on the FAS and PPS, with the former being the basis for the primary efficacy analysis.' The secondary endpoints on PPS will not be assessed in this SAP.

In protocol, it states: The missing TG value at Months 6 or 12 will be imputed using an imputation model that contains the following variables: baseline fasting TG, fasting TG at each post-baseline visits and the multiple imputation will be stratified by treatment group ([Schafer 1997](#); [Schafer 1999](#)). The missing value imputation method for the primary analysis is updated in the SAP as below:

The retrieved dropouts multiple imputation approach will be used for imputing missing values after discontinuation for the primary efficacy analysis. If there is not a sufficient number of retrieved dropouts, a placebo washout multiple imputation approach will be used for imputing missing values for the primary efficacy analysis.

## 6 APPENDICES

### 6.1 Appendix A – Grading Scale for Selected Lab Analytes with Abnormal Values

Parameter	Unit	Mild	Moderate	Severe
Hemoglobin Decreased (Anemia)	g/dL	< LLN - 10.0	< 10.0–8.0	< 8.0
WBC Decreased	cell/mm 	< LLN - 3,000	< 3,000–2,000	< 2,000
Platelets Decreased	cell/mm 	< LLN - 75,000	< 75,000–50,000	< 50,000
Creatinine Increased		> ULN-1.5 × ULN if baseline normal > 1.0–1.5 × baseline if baseline abnormal	> 1.5–3.0 × ULN if baseline normal > 1.5–3.0 × baseline if baseline abnormal	> 3.0 × ULN if baseline normal > 3.0 × baseline if baseline abnormal
ALT, AST Increased		> ULN-3.0 × ULN if baseline normal > 1.5–3.0 × baseline if baseline abnormal	> 3.0–5.0 × ULN if baseline normal > 3.0–5.0 × baseline if baseline abnormal	> 5.0 × ULN if baseline normal > 5.0 × baseline if baseline abnormal
Total Bilirubin Increased		> ULN-1.5 × ULN if baseline normal > 1.0–1.5 × baseline if baseline abnormal	> 1.5–3.0 × ULN if baseline normal > 1.5–3.0 × baseline if baseline abnormal	> 3.0 × ULN if baseline normal > 3.0 × baseline if baseline abnormal

Version:	1
Version Date:	18 Oct 2023
Title:	

